Title: Osteopathic Manipulative Treatment in the Third Trimester of Pregnancy

NCT#: NCT06570395

Date: 05/27/2025

Abstract/Intro

Osteopathic Manipulative Therapy (OMT) is a hands-on approach to treating conditions that affect all areas of the body. Physicians trained in OMT (Doctors of Osteopathic Medicine or DO) use OMT to correct structural imbalances in the body, relieve pain, and improve circulation. It is not only used as a treatment modality, but also to diagnose and prevent disease and improve overall functioning. There are over 40 OMT techniques that all involve gentle manipulation of the muscles, soft tissues, and joints in several ways to optimize alignment, improve blood flow, restore balance, and improve range of motion ("Osteopathic Manipulative Therapy & OMT." Cleveland Clinic). Research shows that manual therapy is equally or more effective in treating pain and improving function versus oral analgesics (Bodine). OMT can decrease cost and improve function in patients with a minimal adverse effect profile.

Some OMT techniques are similar to those used by chiropractors, physical therapists, and massage therapists. What makes it unique is that osteopathic physicians are trained to apply the philosophies of OMT with their comprehensive medical training of all body systems to specifically adapt the treatment to each individual patient. They incorporate their vast knowledge of pathology and physiology with the philosophy that the body can self-heal and self-regulate.

While OMT is most known for its application in treating pain, it truly involves holistic examination of the whole patient – body, mind, and spirit – and can be applied to any situation that places stress upon the body. It is also adjusted based on the patient's condition, age, weight, and other characteristics to yield personalized treatment that can be an adjunct to treatment for virtually any disease or condition (Roberts). Other OMT applications include relieving asthma, irritable bowel syndrome, fibromyalgia, migraines, carpal tunnel syndrome, and sports-related injuries. In addition to the indications listed above, there is a growing body of research surrounding the use of OMT in pregnancy and its use in treatment and prevention of complications peripartum.

Problem and/or Purpose Statement- Objective of the Research

The current practice of obstetrics does not often incorporate the use of OMT in pregnancy to treat pain or prevent complications during and after delivery, despite evidence that it is safe. We believe there is a need to focus attention on the effect of OMT on the rates of specific adverse events in labor and delivery.

Question: Does OMT during the third trimester of pregnancy improve delivery outcomes including: decreased labor times, less utilization of analgesics, fewer incidences of meconium fluid and perineal lacerations, and reduced risk of conversion to c-section or operative vaginal delivery?

Explanation of need for the study: Though all research has shown that OMT is safe in pregnancy there has been conflicting data on its benefits during the peripartum period. Additional research is needed to show its utility in decreasing labor times and need for analgesics during labor and reducing incidence of

adverse outcomes including perineal lacerations and conversion to c-section and operative vaginal delivery.

How results will contribute to existing knowledge: Our study will add to the growing body of knowledge about OMT during pregnancy and its potential benefits outside of musculoskeletal pain relief.

Background information

Hypothesis: OMT in the third trimester of pregnancy will reduce incidence of adverse outcomes including: conversion to operative vaginal deliveries (OVD) and cesarean sections (CS), decrease the use of analgesics during labor, shorten labor times and reduce the incidence of meconium fluid. Conversion to cesarean section or operative vaginal delivery is sometimes unavoidable for the safety of both the mother and baby but they do come with their own set of risks. C-sections incur the same risks of other operative procedures including hemorrhage, infection, embolism, and damage to other organs (“C-Section” Cleavland Clinic). Risks associated with operative vaginal deliveries, those performed with forceps or vacuum devices, have the risk of tears to the muscles of the vagina or rectum, which may cause difficulty urinating or urinary incontinence. Risks to the baby include scalp edema, bruising leading to jaundice, cephalohematoma, and skull fractures (“Forcep Delivery” and “Vacuum Extraction Delivery,” Cleavland Clinic).

Theoretical Framework- Present Knowledge

Current data supports that OMT is safe for use in pregnant patients. Osteopathic manipulative treatment is used daily to treat patients at the Longmeadow Primary Care Residency Clinic.

Literature Review

A retrospective study published in 2003, looked at the medical records of women from 4 different cities who did receive prenatal OMT compared to women in those same cities who did not receive prenatal OMT. The study looked for the occurrence of meconium fluid, preterm delivery, operative vaginal delivery (forceps delivery) and conversion to c-section (King et al). The types of OMT used varied based on the needs of the patient and the individual osteopathic structural examination. Two of the study sites had a single physician who performed OMT on all the study participants while the other two sites used several staff physicians and residents to perform OMT on the study participants. The study found that the participants who received OMT were significantly older (28.32yo vs 26.89yo) than those who did not receive OMT and yet they had fewer complications of labor and delivery than the group that did not receive OMT (King et al). The study concluded that if older women have a higher incidence of poor labor and delivery outcomes it should be even harder to obtain favorable study outcomes among this age group. This study also found that OMT was consistently associated with favorable labor outcomes and lower rates of meconium fluid, preterm delivery, and operative vaginal delivery. While the use of several physicians could introduce error into the study the positive results suggest further validity of OMT in the setting of labor and delivery.

A literature review in 2012 by John M. Lavelle, DO, looked at the ability of OMT to improve the quality of life of pregnant women by treating somatic dysfunction caused by the rapid changes in the maternal body. He stated that data supported the benefit of OMT in lower back and pelvic pain in pregnancy but

also stated that there were not enough randomized controlled trials to support the use of OMT in the prenatal patient (Lavelle).

A systematic review of OMT in gynecology and obstetrics (Ruffini et al.) concluded that the small number of studies and high risk of bias prevented any indication on effect of OMT care. This literature review looked at 24 studies ranging in topics from low back and pelvic pain in pregnancy to infertility and dysmenorrhea. It also looked at analgesic use during labor and delivery. The authors concluded that OMT could be effective on pregnancy related back pain but was uncertain in other gynecologic and obstetric conditions. Only three studies listed adverse events following OMT, lacking sufficient data for analysis (Ruffini et al).

The Pregnancy Research on Osteopathic Manipulation Optimizing Treatment Effects (PROMOTE) study from 2016 (Hensel et al) studied the application of OMT to manage pain and dysfunction in pregnant patients during their third trimester. Patients were randomized to either OMT, usual care plus placebo ultrasound, or usual care and the incidence of high-risk status and labor and delivery outcomes were analyzed. Results showed that high-risk status was less likely to develop in patients who received OMT, and the protocol was also safe regarding labor and delivery outcomes. OMT did not increase the risk of precipitous labor, c-section or operative vaginal delivery. There was also no increase in need for episiotomy, incidence of perineal laceration or meconium fluid when compared to the usual care or the usual care plus placebo groups. Interestingly, the OMT group was 2.3 times more likely to experience prolonged labor when compared to the participants of the usual care group and 4 times more likely to experience prolonged labor when compared to the participants in the usual care plus placebo. It is important to note that the difference in labor durations were not statistically significant in relation to any of the safety outcomes (Hansel et al).

A prospective study was completed in 2019, looking at the effects of OMT on the duration of labor in the inpatient setting (Martingano et al). In this study 100 patients were enrolled, with 50 receiving adjunct OMT along with standard labor management from osteopathic physicians. These patients were matched to 50 control patients, who received standard labor management alone from allopathic physicians. Patients in the OMT group were treated once daily with a standardized protocol including: suboccipital decompression, thoracic inlet release, rib raising, paraspinal inhibition, and sacral inhibition. Every OMT patient received every treatment each day that they were admitted. The study looked at labor duration, meconium fluid, and conversion to a c-section due to failure to progress or lack of descent. All 100 patients in this study received an epidural and oxytocin augmentation of labor. The average duration of labor for controls was 16.57 hours versus 11.34 hours in the OMT group (Martingano et al). These results are in direct contradiction with the former retrospective study completed by Hansel et al in 2016.

Case Study Protocol

Background:

- a. Previous research as described in above literature review
- b. Does OMT in the 3rd trimester of pregnancy shorten duration of labor?
- c. Does OMT in the 3rd trimester of pregnancy reduce risk of perineal laceration, meconium fluid, operative vaginal delivery, or conversion to c-section?
- d. Does OMT in the 3rd trimester of pregnancy reduce analgesic use during labor?

Design:

- a. Pregnant patients who are 34 weeks to delivery will be recruited through Southwest Michigan Women's Clinic and Cass Community Clinic in Niles, Intercare (Benton Harbor), South Shore Women's Health (Saint Joseph), and BellaNova (Saint Joseph, MI), using referrals and flyers distributed by providers in those offices
- b. Patients who wish to participate will call the Longmeadow Primary Care Clinic (number listed on flyer) to schedule an appointment.
- c. Participants must discuss their participation in the study with their obstetrical provider and provide a signed information brochure at their first appointment. Signed brochures will be scanned into the patient's chart.
- d. Patients will be consented using a tablet in the lobby of the Longmeadow Primary Care Residency Clinic or with [name], consent form attached

- h. Magnesium sulfate received for seizure prophylaxis in setting of preeclampsia w/ severe features or severe gestational HTN
- i. Scheduled c-section due to prior OB conditions

Data Collection:

- a. data to be collected via EPIC charting completed by nurse and obstetrical provider
 - i. maternal age
 - ii. parity
 - iii. gestational age
 - iv. number of OMT treatments received
 - v. Types of OMT treatments received
 - vi. preterm delivery before 37 weeks (if applicable)
 - vii. duration of labor
 - viii. meconium amniotic fluid

- ix. perineal laceration occurrence and degree
- x. epidural and other analgesic use
- xi. need for operative vaginal delivery
- xii. need for conversion to c-section
- xiii. APGAR scores
- b. Data will only be available to primary and secondary investigators
- c. Data will be stored in a password protected excel sheet on a protected server
- d. Identifying data will not be shared or used in future write ups

Data Analysis:

Unknown at this time, dependent on available software and data

Study Limitations:

- a. Propensity of OB providers to convert to CS/OVD
- b. Patient preference for OMT/experience with OMT
- c. Age of patient
- d. Pre-existing physical activity may change outcomes and participation
- e. Body habitus
- f. Limited number of patients in study
- g. Protections in vulnerable patient population

Ethical Considerations:

Benefits: (Carnes, Mars et al. 2010)

- Reduced pain
- Increased mobility
- Reduced lower extremity swelling
- Decreased health care cost

Risks: (Carnes, Mars et al. 2010)

- Increased muscle soreness following treatment- short term, minimal severity, diminished in days
- Localized tenderness/stiffness
- Headaches

Absolute Contraindications: (Carnes, Mars et al. 2010)

General issues

1. No permission given by patient
2. Contraindications have not been established
3. No thorough medical history and physical examination have been conducted

General Medical Conditions

1. Patient has an underlying medical/surgical emergency
2. Acute abdominal pain
3. Sudden unexplained nausea, vomiting or diarrhea

Cardiovascular disorders

1. Hypertensive crisis with BP >190/110 bpm
2. Tendency to collapse (low BP, low BMI)
3. Untreated cardiac insufficiency and arrhythmia

Neurological/Neurovascular disorders

1. Suspected vascular occlusions
2. Acute, intense headache
3. Acute neck stiffness
4. Strong unexplained vertigo
5. Acute paresthesia/paralysis
6. Cauda-Equina Syndrome
7. Sudden visual disturbances

Obstetric & Gynecological disorders

1. Symptoms that risk fetal loss such as contractions and vaginal bleeding
2. Abnormal prenatal tests during pregnancy that OB deems unsuitable

Psychiatric disorders

1. Untreated psychosis
2. Underage or mentally incompetent patients who are unable to give consent
3. Post-traumatic stress
4. Suicidal patients

Adverse Event Reporting

Adverse events that are non-serious will be reported in the Annual Report or Withdrawal of IND report to the FDA, and in the Continuing Review to the IRB. Serious or life-threatening adverse events directly attributable to the test article will be reported to the FDA and IRB in a prompt manner, based on IRB policies. In general, a serious adverse event (SAE) will meet any of the following conditions:

- 1) results in death;
- 2) is life-threatening (places the subject at immediate risk of death from the event as it occurred);

- 3) results in hospitalization or prolongation of existing hospitalization;
- 4) results in persistent or significant disability/incapacity;
- 5) results in a congenital anomaly or a birth defect; or
- 6) based upon appropriate medical judgment, may jeopardize the subject's health and may require medical or surgical intervention to prevent a severe outcome.

SAE reporting will be based on whether the SAE is possibly, probably or definitely related to the administration of this test article. Abnormal laboratory values will be reported if associated with a clinical abnormality.

References

“Osteopathic Manipulative Therapy & OMT.” Cleveland Clinic, my.clevelandclinic.org/health/treatments/9095-omt-osteopathic-manipulation-treatment. Accessed 4 Aug. 2023.

Bodine WA. Osteopathic Manipulative Treatment: A Primary Care Approach. *Am Fam Physician*. 2019 Feb 15;99(4):214. PMID: 30763051.

“C-Section (Cesarean Section): Procedure, Risks & Recovery.” C-Section, Cleavland Clinic, my.clevelandclinic.org/health/treatments/7246-cesarean-birth-c-section. Accessed 5 Oct. 2023.

“Forceps Delivery: What to Expect, Risks & Recovery - Cleveland Clinic.” Forceps Delivery, Cleavland Clinic, my.clevelandclinic.org/health/treatments/23260-forceps-delivery. Accessed 5 Oct. 2023.

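### The data list has no field for fetal death, neonatal death or neonatal intensive-care admission, and the serious-event criteria do not say whether they cover the fetus and newborn

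*Protocol*

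**What the plan says.** Data Collection (item a) lists 13 items to be taken from the chart. Apgar is the only direct measure of the newborn. Gestational age, preterm delivery and meconium also bear on the fetus or newborn. Design (item l) rules out follow-up and contact after delivery, and makes Epic the source of all data.

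Adverse Event Reporting gives six criteria for a serious event:

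- Criterion 1: "results in death".
- Criterion 2: "is life-threatening (places the subject at immediate risk of death from the event as it occurred".
- Criterion 3: "results in hospitalization or prolongation of existing hospitalization".
- Criterion 4 concerns disability or incapacity and names no person.
- Criterion 5: "results in a congenital anomaly or a birth defect; or".
- Criterion 6 is an event that "may jeopardize the subject's health and may require medical or surgical intervention to prevent a severe outcome".

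The section also holds two rules on when to report. The first is: "Serious or life-threatening adverse events directly attributable to the test article will be reported to the FDA and IRB in a prompt manner". The second is: "SAE reporting will be based on whether the SAE is possibly, probably or definitely related to the administration of this test article".

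Fetal loss appears once, as an item under Absolute Contraindications, Obstetric & Gynecological disorders: "Symptoms that risk fetal loss such as contractions and vaginal bleeding".

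**The concern.** Treatment is given in late pregnancy, so there are two people to whom harm could come. The protocol acknowledges this in several places. It treats symptoms that put the pregnancy at risk as a reason not to give OMT. Its Hypothesis paragraph lists injuries to the baby from operative vaginal delivery. Its Literature Review cites a randomized third-trimester study in which prolonged labor was 2.3 times (against usual care) and 4 times (against usual care plus placebo) as likely with OMT. The same review section describes a systematic review in which only three studies listed adverse events, too few to analyse.

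The most serious newborn outcomes are nevertheless missing from the data list, and the serious-event section leaves open whether they fall within it. Two things are at stake. The finished study could say nothing, in either group, about fetal death, neonatal death or intensive-care admission. And the person deciding whether to report such an event would have unclear text to work from.

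**Working it through.** The protocol states no sample size, event rate or power, so there is no figure to reproduce. The check is a count by reading.

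**Step 1: the extraction list (Data Collection, item a, i to xiii).**

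| Type of item | Items | Count |
|---|---|---|
| Direct newborn measure | Apgar | 1 |
| Also bears on fetus or newborn | gestational age, preterm delivery, meconium | 3 |
| Mother, treatment or course of delivery | age, parity, number of OMT sessions, types of OMT, labor duration, laceration, analgesia, operative vaginal delivery, cesarean | 9 |
| Fetal death, neonatal death, neonatal intensive care | none | 0 |

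1 + 3 + 9 + 0 = 13, so the list is fully accounted for and all three outcomes are absent. Apgar is not a substitute. The protocol does not say how a stillbirth would be entered, and an Apgar score does not show a newborn who deteriorates later.

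**Step 2: is there another source?** Design (item l) leaves only Epic and excludes contact after delivery. The document names no other source, so an outcome not on the list is not available for the comparison.

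**Step 3: whose event counts as serious?**

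| Wording | Criteria | Count |
|---|---|---|
| Must concern the child by its content | 5 | 1 |
| Tied to the subject, who is not defined | 2, 6 | 2 |
| Names no person | 1, 3, 4 | 3 |

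1 + 2 + 3 = 6. A fetal or neonatal death can be read into criterion 1, and a newborn's admission into criterion 3. A life-threatening event in the newborn falls under criterion 2 only if the newborn counts as a subject, which the text does not settle.

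**Step 4: the reporting rules.** The first demands direct attribution to OMT. The second includes events that are only possibly related. A stillbirth some days after a session could meet the second and fail the first. Even if the criteria clearly covered the child, which rule applies would still decide whether the event is reported promptly.

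**The case against.** The strongest reply is that nothing here is forbidden or contradicted. The study questions concern labor duration, analgesia, lacerations, meconium and mode of delivery. Safety is taken as a premise, and a protocol need not extract every neonatal outcome. The serious-event list is stock wording, introduced as a general guide and tied to IRB policies that are not shown. Those policies may well cover the newborn.

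Much of this stands, and it rules out several stronger readings:

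- A reader might infer that the child is covered only through birth defects and Apgar. That is wrong: preterm delivery, gestational age and meconium are also collected.
- A reader might infer that a stillbirth or a newborn's intensive-care admission need not be reported. The text does not support this, because criteria 1, 3 and 4 are not limited to the mother. The defect is ambiguity, not exclusion.
- A reader might infer that the protocol names fetal loss as its safety concern. It does not. Fetal loss occurs once, within a contraindication, and is neither an outcome nor a safety objective.
- The cited finding on prolonged labor does not show harm to newborns. The protocol reports that the differences in labor duration were not statistically significant in relation to any safety outcome. It is a reason to look, no more.

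The reply does not remove the gap in the data list. That list is fixed in the protocol, and no policy on event reporting would put these outcomes into the group comparison.

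**Conclusion.** The point holds in a limited form. As written, the study cannot compare the OMT and control groups on fetal death, neonatal death or neonatal intensive-care admission: none of the three is among the 13 items, and there is no other source. The serious-event criteria do not state whether they cover the fetus and newborn, so such events may go unreported. The two relatedness thresholds add to that risk.

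The size is the count itself: three outcomes without a field, two criteria resting on an undefined term, and two reporting rules that differ. A reader might want an expected number of missed events, but the protocol gives neither a sample size nor event rates, so none should be quoted.

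The verdict assumes that the 13 items are the whole extraction and that no unseen policy defines the subject. If an IRB policy does define it, the ambiguity about reporting falls away and the gap in the data remains. Since women join the OMT group by their own choice, the added fields would support a descriptive comparison, not proof of safety. This is an inexpensive improvement worth making, not a flaw that invalidates the study.

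**What to change.** 1. Add three fields to Data Collection, for every birth in both groups: fetal death, neonatal death before discharge, and admission to neonatal intensive care.
2. Record the date of each OMT session. At present only the number and types of treatments are listed. With dates, each such event in the OMT group can be listed with the days since the last session.
3. State in Adverse Event Reporting that the serious-event criteria apply to the woman, the fetus and the newborn until discharge.
4. Reconcile the two relatedness thresholds in that section. Widening the criteria alone would not secure reporting.

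The cost is a small amendment to the data list and a few sentences of text, with no extra visits or patient contact. There are two downsides. Data are now to come from charting by the nurse and obstetrical provider, and some of the new items may sit in the newborn's record, so the sponsor may need to confirm that the control-group waiver reaches that record. And there will be somewhat more reporting to the IRB.
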